### **3.5 Purpose and timing of interim analyses/design adaptations**

Not Applicable

### **3.6 Risks and benefits**

The risk to subjects in this trial will be minimized by compliance with the eligibility criteria and study procedures, close clinical monitoring, and the provision of rescue options.

#### **3.6.1 Risks**

Experience in the PARADIGM-HF trial, both in the run-in period as well as the double-blind randomization period, indicated that the major risks associated with the treatment of sacubitril/valsartan are renal dysfunction, [426 (10.14%) in 4203 patients in the double-blind treatment period], hyperkalemia, [488 (11.61%) in 4203 patients in the double-blind treatment period], and hypotension [740 (17.61%) in 4203 patients in the double-blind treatment period].

In PARADIGM-HF, patients treated with enalapril experienced these events at a similar rate with the exception of hypotension; renal dysfunction, [487 (11.52%) in 4229 patients in the double-blind treatment period]; hyperkalemia, [592 (14%) in 4229 patients in the double-blind treatment period]; and hypotension, [506 (11.97%) in 4229 patients in the double-blind treatment period]. Results from the TITRATION study indicated that patients whom are ACE or ARB naïve are at an increased risk of experiencing these adverse events.

In this study, the risk of experiencing renal dysfunction, hyperkalemia, and hypotension are mitigated by appropriate up-titration of the drug every two weeks. The risks are further mitigated by appropriate inclusion and exclusion criteria. Patients entering into the study must have an SBP of at least 140 mmHg if not treated for hypertension or a SBP of >105 mmHg if

they are currently on treatment. Additionally, patients are excluded if they have an eGFR < 30 ml/min/1.73 m^2 or a potassium > 5.2 mEq/L at screening.

Drug to drug interactions are known to occur with concomitant use of ACE/ARB/NEP and renin inhibitors. See [Section 5.5.8](#) for prohibited medications. Patient will be provided with study treatment instructions and their medication histories will be reviewed at Screening and all subsequent visits.

Sacubitril/valsartan, [19 (0.5%) in 4203 patients in the double-blind treatment period of PARADIGM-HF] and enalapril 10 (0.2%) in 4229 patients in the double-blind treatment period of PARADIGM-HF] may also cause angioedema. The risk of developing angioedema is increased if patients take both an ACEi and sacubitril/valsartan. To decrease this risk, patients will be required to undergo a 36-hour washout prior to randomization as well as the open-label treatment epoch to minimize the interaction between an ACEi and sacubitril/valsartan in potentiating the development of angioedema.

In the PARADIGM-HF study, sacubitril/valsartan reduced the risk of CV death and HF hospitalization versus enalapril. In the US, sacubitril/valsartan is approved and indicated to reduce these risks in patients with chronic heart failure (NYHA class II-IV) and reduced ejection fraction. Due to this, the double-blind treatment epoch is limited to 12 weeks to minimize the chance of exposure to standard treatment with enalapril. Thereafter, all patients will have the opportunity to receive 12 weeks of open-label sacubitril/valsartan. It should be noted that the population of patients studied in PARADIGM-HF included NYHA class II-IV patients that were all on either ACEi or ARBs prior to study enrollment. The population of patients included in this study is different than that of PARADIGM-HF.

There is a chance a patient may develop signs and symptoms of worsening heart failure for which the investigator would like to administer appropriate therapy. Appropriate adjustments, intensifications, or additions to concomitant medications should be considered. If needed, the investigator can choose to withdraw the patient from the study to initiate treatment with sacubitril/valsartan, ACEi, or ARBs if the investigator believes this to be appropriate treatment. Rescue options are provided in [Section 5.5.6](#).

In addition to investigational treatment, all patients will be allowed to continue receiving the rest of their background cardiovascular (CV) medications throughout the study. Patients will be randomized to study treatment only after the investigator has confirmed the patient is on stable treatment with guideline-directed therapy for HFrEF, other than ACEis and ARBs, which will ensure that patients are receiving appropriate treatment for their heart failure.

The study procedures and assessments for this study are either non-invasive or minimally invasive (venipuncture for blood draws) and are considered low risk.

### **3.6.2 Benefits**

All patients will receive active treatment for heart failure that reduces the risk of mortality and hospitalizations. After completion of the double-blind treatment epoch, all patients will have the opportunity to receive 12 weeks of open-label sacubitril/valsartan, a drug which has been proven to reduce the risks of CV death and HF hospitalization versus enalapril.

This study is the first clinical trial to treat NYHA Class I asymptomatic heart failure patients with sacubitril/valsartan. Data collected may determine if heart failure progression can be prevented. Additionally, patients with NYHA Class I heart failure wouldn't otherwise have access to sacubitril/valsartan as the drug is not approved for use in these patients.

Study assessments and frequent visits will provide close monitoring of patients' conditions and may provide information that may benefit heart failure patients in the future.

## 4 Population

The study population will consist of out-patient male and female patients,  $\geq 50$  years of age with HFrEF  $\leq 40\%$  who have a history of hypertension. The goal is to randomize a total of approximately 432 patients to sacubitril/valsartan or enalapril in a 1:1 ratio at approximately 80 centers in the United States. The estimated screen failure rate is 25%. Approximately 575 patients will be screened.

At the time of randomization, patients will have been on stable treatment with guideline-directed therapy for HFrEF, other than ACEis and ARBs, and on an optimal medical regimen to effectively treat co-morbidities such as HTN, DM and coronary artery disease. Patients will have met all other inclusion and none of the exclusion criteria.

### 4.1 Inclusion criteria

Patients/subjects eligible for inclusion in this study must fulfill all of the following criteria at screening and randomization:

1. Written informed consent must be obtained before any assessment is performed.
2. Men and women  $\geq 50$  years of age.
3. History of HTN and one of the following at BOTH screening and pre-randomization:
  - a. SBP  $> 105$  mm Hg on antihypertensive medication.
  - b. SBP  $\geq 140$  mm Hg and NOT on antihypertensive medication.
4. Patients diagnosed with heart failure NYHA class I-III and reduced ejection fraction  $\leq 40\%$  as determined by any local measurement made within the past 12 months using echocardiography, MUGA, CT scanning, MRI, ventricular angiography or single-photon emission computed tomography (*SPECT*), provided no subsequent measurement above 40%. Patients who have had an intervening medical event (e.g. myocardial infarction) or procedure (e.g. revascularization, cardiac resynchronization), must have a reassessment of EF  $\geq 3$  months following the event to ensure that eligibility criteria are still met.
5. On stable doses of treatment with guideline-directed therapy, other than ACEis and ARBs, prior to randomization.
  - a. If the patient is currently taking an ACEi, a 36-hour washout is required prior to randomization (Visit 2).
  - b. If the patient is currently taking an ARB, they must discontinue the ARB before initiation of study treatment however, washout is not required.
6. On an optimal medical regimen to effectively treat co-morbidities such as HTN, DM, and coronary artery disease. Investigators should make every effort to control a patient's BP in accordance with local treatment guidelines and investigator judgment.

## 4.2 Exclusion criteria

Patients fulfilling any of the following criteria, at screening and prior to randomization, are not eligible for inclusion in this study for purposes of safety measures. No additional exclusions may be applied by the investigator, in order to ensure that the study population will be representative of all eligible patients/subjects.

1. History of hypersensitivity to any of the study drugs, including history of hypersensitivity to drugs of similar chemical classes, or allergy to ACEis, ARBs, or NEP inhibitors as well as known or suspected contraindications to the study drugs.
2. Previous history of intolerance to sacubitril/valsartan, ACEi or ARB standard of care doses despite appropriate and gradual up-titration.
3. History of angioedema, drug-related or otherwise.
4. Requirement of treatment with both ACE inhibitor and ARB.
5. Current or prior treatment with sacubitril/valsartan.

Patients/subjects taking medications prohibited by the protocol (see [Section 5.5.8, Table 5-9](#)).

6. Use of other investigational drugs within 5 half-lives of enrollment, or within 30 days until the expected pharmacodynamic effect has returned to baseline, whichever is longer.
7. Currently enrolled in any other clinical trial involving any investigational agent or investigational device.
8. DBP > 100 mm Hg at screening or at randomization.
9. eGFR < 30 ml/min/1.73 m^2 (calculated by the Modification of Diet in Renal Disease formula) at screening.
10. Potassium > 5.2 mEq/L at screening.
11. Documented or untreated ventricular arrhythmia with syncopal episodes within the 3 months prior to Screening/Baseline (Visit 1).
12. Persistent or permanent atrial fibrillation at Screening/Baseline (Visit 1).
13. Acute coronary syndrome, stroke, transient ischemic attack, cardiac, carotid or other major CV surgery, percutaneous coronary intervention (PCI) or carotid angioplasty within the 3 months prior to first Screening/Baseline (Visit 1).
14. Implantation of a cardiac resynchronization therapy pacemaker (CRT-P) or a cardiac resynchronization therapy defibrillator (CRT-D) or upgrading of an existing conventional pacemaker or an implantable cardioverter defibrillator (ICD) to CRT device within 3 months prior to first visit or intent to implant such a device.
15. Heart transplant or ventricular assistance device (VAD) or intent to transplant (on transplant list) or implant a VAD.
16. Coronary or carotid artery disease likely to require surgical or percutaneous intervention within the 6 months after Visit 1.
17. Hemodynamically significant aortic stenosis/regurgitation or mitral valve disease other than mitral valve regurgitation related to LV dilation.
18. Presence of other hemodynamically significant obstructive lesions of left ventricular outflow tract, including aortic and sub-aortic stenosis.
19. Isolated right HF due to severe pulmonary disease.

20. Diagnosis of peripartum or chemotherapy induced cardiomyopathy within the 12 months prior to Screening/Baseline (Visit 1).
21. Treatment with Vaughn Williams Type Ic anti-arrhythmic agents (e.g., Flecainide, propafenone, moricizine).
22. Symptomatic bradycardia or second or third degree heart block without a pacemaker.
23. History of familial long QT syndrome or known family history of Torsades de Pointes
24. History of malignancy of any organ system (other than localized basal cell carcinoma of the skin), treated or untreated, within the past year with a life expectancy of less than 1 year.
25. Any surgical or medical condition which might significantly alter the absorption, distribution, metabolism, or extraction of study drug, including but not limited to any of the following:
  - a. History of active inflammatory bowel disease during the 12 months prior to Screening/Baseline (Visit 1)
  - b. History of peptic ulcer disease without successful eradication of *H. pylori*.
  - c. Gastrointestinal/rectal bleeding during the 3 months prior to Screening/Baseline (Visit 1).
  - d. Current treatment with cholestyramine or colestipol resins.
26. Known hepatic impairment (as evidenced by total bilirubin > 3 mg/dL, or increased ammonia levels, if performed), or history of cirrhosis with evidence of portal hypertension such as varices.
27. Bilateral renal artery stenosis.
28. Inability to secure technically adequate baseline tonometry study.
29. Pregnant or nursing (lactating) women, where pregnancy is defined as the state of a female after conception and until the termination of gestation, confirmed by a positive hCG laboratory test.
30. Women of childbearing potential, defined as all women physiologically capable of becoming pregnant, unless they are using highly effective methods of contraception during dosing and for 7 days after stopping of study medication. Highly effective contraception methods include:
  - a. Total abstinence (when this is in line with the preferred and usual lifestyle of the subject). Periodic abstinence (e.g., calendar, ovulation, symptothermal, post-ovulation methods) and withdrawal are not acceptable methods of contraception
  - b. Female sterilization (have had surgical bilateral oophorectomy with or without hysterectomy) total hysterectomy or tubal ligation at least six weeks before taking investigational drug. In case of oophorectomy alone, only when the reproductive status of the woman has been confirmed by follow up hormone level assessment
  - c. Male sterilization (at least 6 months prior to screening). For female subjects on the study, the vasectomized male partner should be the sole partner for that subject
  - d. Use of oral, (estrogen and progesterone), injected or implanted hormonal methods of contraception or placement of an intrauterine device (IUD) or intrauterine system (IUS) or other forms of hormonal contraception that have comparable efficacy (failure rate <1%), for example hormone vaginal ring or transdermal hormone contraception

In case of use of oral contraception, women should have been stable on the same pill for a minimum of 3 months before taking investigational drug.

31. Women are considered post-menopausal and not of child bearing potential if they have had 12 months of natural (spontaneous) amenorrhea with an appropriate clinical profile (e.g. age appropriate, history of vasomotor symptoms) or have had surgical bilateral oophorectomy (with or without hysterectomy), total hysterectomy or tubal ligation at least six weeks ago. In the case of oophorectomy alone, only when the reproductive status of the woman has been confirmed by follow up hormone level assessment is she considered not of child-bearing potential.
32. Sexually active males must use a condom during intercourse while taking drug and for 7 days after stopping study medication and should not father a child in this period. A condom is required to be used also by vasectomized men in order to prevent delivery of the drug via seminal fluid.

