### 3 Investigational plan

#### 3.1 Study design

This study will use a multicenter, randomized, double-blind, double-dummy, parallel group, active-controlled, forced titration, 12-week design in patients with heart failure and reduced left ventricular ejection fraction (LVEF)  $\leq 40\%$ . The study duration is a maximum of 30 weeks, including the screening epoch, with 8 scheduled outpatient visits.

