##### Screening epoch

Patients will enter a screening epoch up to 6 weeks, beginning with Baseline (Visit 1) at - 42 to -1 day(s) prior to randomization to assess eligibility requirements and to confirm patients are on stable treatment with guideline-directed therapy for HFrEF, other than ACEis and ARBs.

- Screening/Baseline echocardiography (echo), ECG and safety labs will be obtained.
- Non-invasive arterial hemodynamics assessments will be obtained specifically within the window of study day -7 to -2 prior to randomization on Day 1 (Visit 2) to ensure quality control and to allow for a repeat study on day -1, if necessary.
- Biomarkers [REDACTED] will be obtained on Day 1 (Visit 2), pre-randomization.
- If the patient is currently taking an ACEi, a 36-hour washout is required prior to randomization (Visit 2).
- If the patient is currently taking an ARB, they must discontinue the ARB before initiation of study treatment however, washout is not required.

Note: Baseline for this study includes assessments performed during Screening and through Day 1 (Visit 2) pre-randomization.

Patients can be randomized as soon as screening criteria are met.

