5.6 Rule of exclusion criteria of analysis sets

Table 1 Protocol deviations that cause patients to be excluded

Deviation ID	Description of Deviation	Exclusion in Analyses
I03	Patient did not have history of HTN and one of the following at BOTH screening and pre-randomization: a. SBP > 105 mm Hg on antihypertensive medication b. SBP \geq 140 mm Hg and NOT on antihypertensive medication	Exclusion from PPS
I04	Patient was not diagnosed with heart failure NYHA class I-III and reduced ejection fraction \leq 40%	Exclusion from PPS
E01	Patient has a history of hypersensitivity to any of the study drugs, including history of hypersensitivity to drugs of similar chemical classes, or allergy to ACEis, ARBs, or NEP inhibitors as well as known or suspected contraindications to the study drugs	Exclusion from PPS
E02	Patient has history of intolerance to sacubitril and valsartan, ACEi or ARB standard of care doses	Exclusion from PPS
E03	Patient has history of angioedema	Exclusion from PPS
E04	Patient requires treatment with both ACE inhibitor and ARB	Exclusion from PPS

Deviation ID	Description of Deviation	Exclusion in Analyses
E12	Patient had a persistent or permanent atrial fibrillation at Screening/Baseline (Visit 1)	Exclusion from PPS
E13	Patient had Acute coronary syndrome, stroke, transient ischemic attack, cardiac, carotid or other major CV surgery, percutaneous coronary intervention (PCI) or carotid angioplasty within the 3 months prior to first Screening/Baseline (Visit 1)	Exclusion from PPS
E14	Patient has an Implantation of a cardiac resynchronization therapy pacemaker (CRT-P) or a cardiac resynchronization therapy defibrillator (CRT-D) or upgrading of an existing conventional pacemaker or an implantable cardioverter defibrillator (ICD) to CRT device within 3 months prior to first visit or intent to implant such a device	Exclusion from PPS
E15	Patient has a heart transplant or ventricular assistance device (VAD) or intent to transplant (on transplant list) or implant a VAD	Exclusion from PPS
E16	Patient has a Coronary or carotid artery disease likely to require surgical or percutaneous intervention within the 6 months after Visit 1	Exclusion from PPS
E17	Patient has a hemodynamically significant aortic stenosis/regurgitation or mitral valve disease other than mitral valve regurgitation related to LV dilation	Exclusion from PPS

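### The 3-month look-backs in exclusions 11 and 13 stop at Visit 1, so a stroke, TIA, other major cardiovascular surgery or syncopal ventricular arrhythmia during the up-to-42-day screening period does not, on the wording, exclude the patient

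*Protocol*

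**What the plan says.** **Length of screening.** Protocol Section 3.1: "Patients will enter a screening epoch up to 6 weeks", starting with Visit 1 between Day -42 and Day -1. The same section states: "The study duration is a maximum of 30 weeks, including the screening epoch".

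**When the exclusions apply.** The lead-in to Section 4.2 applies the list at screening and again before randomization, gives safety as the purpose, and adds: "No additional exclusions may be applied by the investigator". Table 6-1 repeats the inclusion/exclusion check at Visit 2.

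**The two look-backs.** Exclusion 11 (ventricular arrhythmia with syncope) counts back 3 months from Visit 1. Exclusion 13 lists acute coronary syndrome, stroke, TIA and cardiac, carotid or other major cardiovascular surgery, and closes with "percutaneous coronary intervention (PCI) or carotid angioplasty within the 3 months prior to first Screening/Baseline (Visit 1".

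**A criterion that names both time points.** Exclusion 8: "DBP > 100 mm Hg at screening or at randomization". Inclusion 3 likewise requires its blood pressure condition at both screening and pre-randomization.

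**SAP.** Section 5.6, Table 1, code E13 carries the same anchor into the Per-Protocol Set rules: "carotid angioplasty within the 3 months prior to first Screening/Baseline (Visit 1". The table has no code for exclusion 11.

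**The concern.** A look-back that ends at Visit 1 is blind to anything that happens afterwards. Repeating the check at Visit 2 does not help, because re-reading a window that closed at Visit 1 gives the same answer. The rule therefore excludes the older event and passes over the newer one.

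What is at stake is mainly patient protection. Section 3.6 relies on the eligibility criteria to limit risk, treatment is force-titrated every 2 weeks from Day 1, and Section 8.4 provides no data monitoring committee. There is also a smaller measurement point. Baseline Zc is taken between Day -7 and Day -2 and biomarkers on Day 1, so a late-screening event could fall just before those baseline measurements or between them.

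**Working it through.** **1. Length of the uncovered interval.** The stated maximum duration confirms the 6 weeks: 6 (screening) + 12 (double-blind) + 12 (open-label) = 30 weeks, as Section 3.1 says. The uncovered interval is thus up to 6 × 7 = 42 days. It would be 0 days if the look-back ran to randomization.

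**2. What the wording does.** Take a 6-week screening. A stroke 80 days before Visit 1 is 80 + 42 = 122 days before randomization, and it excludes. A stroke on Day -1 is one day before randomization, and no exclusion names it.

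**3. Which screening-period events are handled elsewhere.**

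| Event after Visit 1 | Other provision | Result |
|---|---|---|
| Infarction, revascularization, cardiac resynchronization | Inclusion 4: EF must be reassessed at least 3 months after the event | Blocked in effect (step 4) |
| Planned CRT device | Exclusion 14, intent clause | Covered |
| Foreseeable coronary or carotid intervention | Exclusion 16 | Covered |
| GI bleeding | Exclusion 25, whose list is stated not to be exhaustive | Can be covered where relevant |
| Persistent AF | Exclusion 12, tested at Visit 1, which Table 6-1 shows as a Day -42 to -1 window | Anchor blurred rather than clearly closed |
| Stroke, TIA, other major cardiovascular surgery | None names it | Open |
| Ventricular arrhythmia with syncope | None names it | Open |

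**4. Why inclusion 4 blocks its examples.** With the SAP Section 2.1.1 conversion, 3 months = 3 × 30.3475 = 91.04 days. Screening lasts at most 42 days. The required wait exceeds it by 91.04 - 42 = 49.04 days, so the reassessment cannot be completed within the same screening period.

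**5. How many patients.** The documents give no event rate. Assume 2 to 5% per year for the open events, a full 42-day screening for everyone, and that every affected patient is still randomized:

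- 432 × 42/365 × 0.02 = 0.99
- 432 × 42/365 × 0.05 = 2.49

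With a 3-week screening these halve to about 0.5 and 1.2.

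**6. Effect on the primary analysis.** The planning SD for the primary variable is 80. Suppose 2.5 of 432 patients had twice that SD (160), an assumption chosen to be severe, with the same mean:

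- share = 2.5/432 = 0.0058
- variance = 80² + 0.0058 × (160² - 80²) = 6,400 + 0.0058 × 19,200 ≈ 6,511
- SD = √6,511 ≈ 80.7

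The SD moves from 80 to about 80.7. Randomization balances these patients between arms in expectation, and the ANCOVA adjusts for baseline Zc.

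**The case against.** The strongest reply is that the protocol plainly intends eligibility to hold at randomization. The Section 4.2 lead-in says so, Section 4 says that patients will then meet none of the exclusions, and Table 6-1 repeats the check. Many exclusions carry no visit at all and rely on the lead-in, so the contrast with exclusion 8 is weak evidence on its own. This shows intent, but it does not move a window that exclusion 13 ties expressly to the first screening visit. It is the reason why the passages should be reconciled.

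Other provisions soften the gap. The intervening event in inclusion 4 is illustrated by examples and could be read to include a stroke or an arrhythmia, although the clause is about whether the EF still qualifies. Inclusions 5 and 6 require stable doses and an optimal regimen at randomization, and exclusion 1 covers known or suspected contraindications. These routes depend on interpretation or discretion; none is a stated rule for these events.

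A reader might go further and infer several things that the documents do not support:

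- **That exclusions 12, 14 and 25c have the same fault.** Step 3 shows other cover for 14 and 25c and a blurred anchor for 12. Nor does the ECG recorded with tonometry offer a ready AF check: Section 6.4.1 uses it for gating and signal averaging, and Section 6.5.9 provides a 12-lead ECG at Screening/Baseline only.
- **That an affected patient must be randomized.** Section 3.1 says patients can be randomized once criteria are met, and SAP Section 2.3.1 lists adverse event and physician decision as screening dispositions.
- **That the Visit 1 anchor keeps patients with syncopal arrhythmia in the Per-Protocol Set.** With no code for exclusion 11, they stay in even if the event came before Visit 1.
- **That the primary result is at risk.** Step 6 shows otherwise, and the primary analysis uses the Full Analysis Set.

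**Conclusion.** The point holds for exclusion 11 and for the stroke, TIA and other major cardiovascular surgery parts of exclusion 13. On the wording, such an event in an interval of up to 42 days before randomization does not exclude the patient, while the same event up to 3 months before Visit 1 does. This is an internal inconsistency between the Section 4.2 lead-in and two of its criteria.

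It is small in numbers. The 1.0 to 2.5 patients rest on unsourced event rates and, for those rates, are an upper range, because not everyone will use 6 weeks and some affected patients will leave screening. The case for acting is patient protection and one clear rule across sites. There is no material threat to power, and no bias between arms is expected.

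**What to change.** In Protocol Section 4.2, reconcile exclusions 11 and 13 with the lead-in so that each look-back also covers the interval from Visit 1 to randomization. In SAP Section 5.6, Table 1, align code E13 with the revised exclusion 13. There is no code for exclusion 11 to edit; whether to add one is a separate decision about the Per-Protocol Set. Leave exclusions 12, 14 and 25c as they are on this ground.

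The cost is a few words in two criteria and one SAP code, plus a few more screen failures. If enrolment has already closed, the protocol wording no longer helps. SAEs are reported from informed consent (Section 5.6.1), so serious events between Visit 1 and Day 1 can be identified and their handling in the Per-Protocol Set stated in SAP Section 5.6 before unblinding.
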